It provides information about procedures for entering participants into the trial, and provides sufficient detail to enable: an understanding of the background, rationale, objectives, trial population, intervention, methods, statistical analyses, ethical considerations, dissemination plans and administration of the trial; replication of key aspects of trial methods and conduct; and appraisal of the trial's scientific and ethical rigour from the time of ethics approval through to dissemination of the results. The protocol should not be used as an aide-memoire or guide for the treatment of other patients. Every care has been taken in drafting this protocol, but corrections or amendments may be necessary. These will be circulated to registered investigators in the trial. Sites entering participants for the first time should confirm they have the correct version through a member of the trial team at MeiraGTx UK II Ltd.

MeiraGTx UK II Ltd. supports the commitment that its trials adhere to the SPIRIT guidelines. As such, the protocol template is based on an adaptation of the Standard Protocol Items: Recommendations for Interventional Trials (SPIRIT) 2012 Statement for protocols of clinical trials (Chan *et Al.* 2013a). The SPIRIT Statement Explanation and Elaboration document (Chan *et Al.* 2013b) can be referred to, or a member of the MeiraGTx UK II Ltd. Clinical Operations team can be contacted for further detail about specific items.

1.1 Compliance

The trial will be conducted in compliance with the approved protocol, the Declaration of Helsinki (2008), the principles of Good Clinical Practice (GCP) as laid down by the Commission Directive 2005/28/EC with implementation in national legislation in the UK by Statutory Instrument 2006/1928 and subsequent amendments, Advanced Therapy Medicinal Products (ATMP) Regulations (EC) No 1394/2007, the Human Tissue (Quality and Safety for Human Application) Regulations 2007, the General Data Protection Regulation 2016/679, and the National Health Service (NHS) Research Governance Framework for Health and Social Care (RGF). US sites will comply with 21 CFR 312 in the Code of Federal Regulations, and the NIH Guidelines for Research Involving Recombinant or Synthetic Nucleic Acid Molecules (November 2013).

The participating sites will inform MeiraGTx UK II Ltd. as soon as they are aware of a possible serious breach of compliance, so that MeiraGTx UK II Ltd. can fulfil its requirement to report the breach if necessary, within the relevant applicable timelines specified in each country in which the study is being conducted. For the purposes of reporting, a 'serious breach' is one that is likely to affect to a significant degree:

- The safety or physical or mental integrity of the participants in the trial, or
- The scientific value of the trial.

1.3 Structured trial summary

Primary Registry and Trial Identifying Number	EudraCT 2016-002290-35
Secondary Identifying Numbers	MeiraGTx UK II Ltd. registration number: MGT006
Source of Monetary or Material Support	MeiraGTx UK II Ltd.
Sponsor	MeiraGTx UK II Ltd.
Contact for Public Queries	[contact]
Contact for Scientific Queries	[REDACTED]
Public Title	Gene Therapy for Achromatopsia (CNGB3)
Scientific Title	An open label, multi-centre, Phase I/II dose escalation trial of an adeno-associated virus vector (AAV2/8-hCARp.hCNGB3) for gene therapy of adults and children with achromatopsia owing to defects in CNGB3
Countries of Recruitment	United Kingdom, United States of America
Health Condition	Achromatopsia
Intervention(s)	Open label, non-randomised, dose-escalation ([REDACTED]), Phase I/II study, by subretinal administration of AAV2/8-hCARp.hCNGB3 in up to 36 participants with achromatopsia owing to mutations in the CNGB3 gene.
Key Inclusion and Exclusion Criteria	
Key Inclusion Criteria:
 
 • Aged 3 years or older (children will be included only once the maximal tolerated dose has been determined) • Achromatopsia caused by mutations in CNGB3 • Evidence of preservation of photoreceptors at the macula • Able to undertake age-appropriate clinical assessments • Willing to give consent for the use of blood and blood components collected throughout the trial for the investigation of immune response to ATIMP 
Key Exclusion Criteria:
 
 • Females who are pregnant or breastfeeding • Intra-ocular surgery within 6 months of screening

Gene Therapy for Achromatopsia (CNGB3)

	
 Ocular or systemic disorder that may preclude subretinal surgery and/or interfere with interpretation of the study results. Participated in another research study involving an investigational therapy for ocular disease within the last 6 months Have any other condition that the PI considers makes them inappropriate for entry into the trial Are unwilling to consider the possibility of entry into a subsequent longer term follow up study
Study Type	Phase I/II, open-label, non-randomised, 2 centre, dose escalation in adults, followed by dose confirmation in adults and children with achromatopsia owing to defects in CNGB3
Date of First Enrolment	Anticipated Q4 2016
Target Sample Size	Up to 36 participants
Primary Outcome(s)	
The primary outcome is safety of subretinal administration of AAV2/8-hCARp.hCNGB3.
 
Safety is defined as the absence of ATIMP-related:
 
 Reduction in visual acuity by 15 ETDRS letters or more Severe unresponsive inflammation Infective endophthalmitis Ocular malignancy Grade III or above non-ocular SUSAR 
Safety will be assessed for 6 months after the intervention in this study, and a further 4.5 years in a separate subsequent study.

Key Secondary Outcomes	
The secondary outcomes are measures of the efficacy of the intervention, which will be performed on an individual participant basis and will be descriptive in nature. Efficacy will be assessed at several time points between 3 to 6 months after the intervention:
 
 Any improvement in visual function from baseline that is greater than the test-retest variation for that test and is sustained for at least two consecutive assessments. Any improvement in retinal function from pre intervention that is greater than the test-retest variation and measurable by electroretinography (ERG). Quality of life measures.

Gene Therapy for Achromatopsia (CNGB3)

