4.1.3 Clinical data

This protocol describes our group's 3rd clinical trial of a gene supplementation therapy for inherited retinal disease using a recombinant AAV (rAAV) vector. In the first gene therapy trial (Bainbridge, *et al* 2008) 12 participants with severe early onset retinal dystrophy caused by mutations in the gene encoding RPE65 were administered rAAV vector subretinally. Vector administration was generally well tolerated and 6 of the 12 participants benefitted with improved visual function to varying

Gene Therapy for Achromatopsia (*CNGB3*)

extents during the first year. However, longer-term follow-up demonstrated that progressive degeneration continued and maximal improvements in retinal sensitivity were not maintained (Bainbridge, *et al* 2015). Similar observations have been described in other independent trials where rAAV2/2 vectors were administered for the same condition by sub retinal administration (Maguire, *et al* 2008; Cideciyan, *et al* 2008; Cideciyan, *et al* 2013). In these studies, subretinal administration of rAAV vectors resulted in visual improvement without significant safety concerns. We are currently investigating the safety and potential efficacy of a new optimized rAAV2/5 vector for delivery of *RPE65* in a trial with a similar design and protocol to this proposed trial [REDACTED] in up to 27 adults and children with retinal dystrophy caused by mutations in *RPE65*.

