4.1.5.5 Risk of surgical adverse effects

The risk of significant surgical adverse effects is similar to the standard surgical care for other common forms of vitreo-retinal disorders. To manage the risk of surgical adverse events, only highly experienced surgeons will perform the procedure. Complications of surgery are typically managed effectively by medication or further surgical intervention but can rarely result in lasting harm to sight. The risk of lasting severe impairment of sight from vitrectomy surgery is approximately 1 in 1000. We have identified some reduction in outer retinal thickness and deterioration in acuity in 2 of the 12 participants in our previous clinical trial, believed to result from temporary retinal detachment which is a deliberate consequence of targeted administration of the vector suspension, but no other significant surgical adverse effects.

Delivery of ATIMP to the subretinal space will be performed by standard surgical vitrectomy. This will involve a 3-port pars plana vitrectomy followed by injection of ATIMP using a fine cannula through small retinotomies, resulting in a temporary retinal detachment. Previous gene therapy clinical trials have shown that the bleb of subretinal ATIMP suspension can be expected to resolve spontaneously over the course of the first 24 to 48 hours postoperatively as the fluid is absorbed by the underlying retinal pigment epithelium.

Gene Therapy for Achromatopsia (*CNGB3*)

Potential complications of surgery specifically include persistence of the subretinal vector bleb, the development of retinal tears, and persistent postoperative intraocular inflammation. We will minimise any risk to visual function by limiting ATIMP delivery to the area of retina most likely to benefit, and by leaving the contralateral eye untreated. Retinal detachment caused by persistent vector bleb or intraoperative retinal tear is expected to occur in fewer than 1 in 100 procedures and can be effectively managed in the majority by retinopexy, with or without intraocular tamponade. Vitrectomy surgery is a standard technique, commonly performed for a wide range of indications. Injection of fluids under the retina is less commonly performed but is a standard step in surgery for subretinal haemorrhage, and an adjunctive technique in the management of retinal detachment.

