5.5.2 Secondary Outcomes

The secondary outcomes are measures of the efficacy of the ATIMP; these will be performed on an individual participant basis and will be descriptive in nature.

- Any improvements in visual function from baseline that are greater than the test-retest variation and are sustained for at least two consecutive assessments.
- Any improvement in retinal function from pre – intervention that is greater than test-retest variation and measurable by electrophysiology (pattern ERG, multifocal ERG or full-field ERG). Quality of life will be measured by the Impact of Visual Impairment (IVI) questionnaire and the EQ5D-5L and EQ5D-Y.

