5.10.3.3 Statistical Methods – Secondary Outcome Analysis

The secondary outcomes are measures of the efficacy of the ATIMP; these will be performed on an individual participant basis and will be primarily descriptive in nature. Standard assessments will be used to measure visual function and established methods of analysis, appropriate for the assessment will be used to evaluate the data. For specialist assessments, data will be analysed by the expert team member(s) who developed the assessment. Final data will be reported descriptively.

Efficacy will be indicated by:

- 1) Any improvement in visual function from baseline that is greater than the test-retest variation for that test and is sustained for at least two consecutive assessments.

CNGB3 Gene Therapy trial for Achromatopsia

2) Any improvement in retinal function from pre – intervention assessment that is greater than test-retest variation and measurable by electrophysiology (pattern ERG, multifocal ERG or full-field ERG).

Measures will be reported individually and aggregated across participants as the proportion who satisfy the above criteria.

Quality of life patient reported outcome measures will be used to correlate a participant’s feeling about their own wellbeing with clinical observations.

Any deviations from the original statistical plan will be approved by the IDMC and described in the final report, as appropriate.

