6.2. Analysis Methods

Summaries by age group, dose level and time point (and study eye when appropriate) using descriptive statistics will be provided for each outcome. Descriptive statistics such as mean, median, standard deviation, minimum, and maximum will be used to summarize continuous variables, and counts and percentages will be used to summarize categorical variables; 95% CIs may be provided for descriptive statistics. Data from each individual will also be plotted across time by age group and dose level for the treated eye compared to the untreated eye, if available. Change from baseline will be summarized, if appropriate.

Mixed linear effects models may be used to assess differences between the treated and the untreated eye with covariates including age group, dose level, time and the interaction of dose level by time. An unstructured correlation structure will be used to model within-subject correlations when possible. Possible transformations of the response (i.e., logarithm) may also be considered for some outcomes.

Sensitivity analyses with demographics such as sex and race may be explored.

Quality of life patient reported outcome measures may be used to correlate a subject's feeling about their own well-being with clinical observations. The IVI-C and IVI-A will be summarized by the 3 domains of reading and accessing information, mobility and independence, and emotional well-being. The EQ-5D-5L⁴ and EQ-5D-Y⁵ will also be summarized (see Attachment 1 for details).

For specialized ophthalmologic assessments, data may be analyzed by the expert team member(s) who are best qualified to analyze and interpret those assessments. Final data will be reported descriptively.

REFERENCES

- Goldstein JE et al. Calibrating the impact of vision impairment (IVI): creation of a sample-independent visual function measure for patient-centered outcomes research. Translational Vision Science & Technology; December 2018; Vol.7, 38
- 2. Lamoureux EL et al. The impact of vision impairment questionnaire: an evaluation of its measurement properties using Rasch analysis. Invest Ophthalmology & Vision Science; November 2006; 47(11):4732-41
- 3. Lamoureux EL et al. The impact of vision impairment questionnaire: an assessment of its domain structure using confirmatory factor analysis and Rasch analysis. Invest Ophthalmology & Vision Science. March 2007; 48(3):1001-6

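### The protocol reports the proportion of participants with a gain beyond test-retest variation, but no matching proportion with a loss

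*Protocol*

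**What the plan says.** Protocol 1.3, 5.5.2 and 5.10.3.3 define two functional indicators of efficacy. For visual function the indicator is "Any improvement in visual function from baseline that is greater than the test-retest variation for that test", sustained over at least two consecutive assessments. For retinal function it is "Any improvement in retinal function from pre – intervention that is greater than test-retest variation and measurable by electrophysiology". Protocol 5.10.3.3 then states: "Measures will be reported individually and aggregated across participants as the proportion who satisfy the above criteria". None of these sections defines a deterioration beyond the same limit.

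Protocol 5.5.1 and 5.10.3.2 and SAP 2.1 define the primary safety outcome. Its only functional component is an acuity loss of 15 ETDRS letters or more, within 6 weeks, judged at least possibly due to the product and not to surgery alone.

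SAP 6.1 says that test-retest variation will no longer be assessed. SAP 6.2 provides means, medians, SDs, minima and maxima, and individual plots of treated against untreated eye. It makes a mixed model optional and adds: "Change from baseline will be summarized, if appropriate". It defines no responder category, upward or downward.

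**The concern.** A proportion that counts one tail cannot separate net benefit from greater spread. If the intervention helps some eyes and harms others, the proportion with a gain is the same as if it helped those eyes and harmed none. A mean change near zero is equally ambiguous, because it fits both no effect and offsetting gains and losses.

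The protocol itself foresees harm to function. Section 4.1.5.5 attributes earlier acuity deterioration to the temporary retinal detachment that delivery deliberately causes. A similar loss judged here to be due to surgery alone would fall outside the primary outcome, whatever its size. Section 4.1.5.8 names rod dysfunction as a risk, and 4.1.5.9 reports macular thinning in 6 of 10 earlier participants, with only an expectation that vision will not suffer. Gains would be counted by a rule and most losses by judgement.

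**Working it through.** The documents give no sample size, power, test-retest SD or success threshold for this rule, so there is no stated figure to reproduce.

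**Step 1. Which losses are counted by a defined threshold?**

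| Loss in the treated eye | Defined count? | Where else it can appear |
|---|---|---|
| Acuity, 15 letters or more, within 6 weeks, at least possibly product-related | Yes: primary outcome | Adverse event (AE) tables, summaries, plots |
| Acuity, 15 letters or more, surgery alone | No | AE tables, summaries, plots |
| Acuity, under 15 letters | No | As above, if recorded as an AE |
| Acuity, after Week 6 | No | As above, if recorded as an AE |
| Contrast, reading, colour, static perimetry (Weeks 12 and 24) | No | As above, if recorded as an AE |
| Full-field and pattern ERG (Week 24) | No | As above, if recorded as an AE |

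Visit times are from Table 2 in Protocol 5.6. AE recording is from Protocol 5.11.3.5 and tabulation from SAP 5.2.

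**Step 2. Does the gain proportion respond to harm?** Assumptions, none from the documents:

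- Within-subject error is normal with SD s.
- The limit is L = 1.96 × √2 × s = 2.77s.
- A gain or loss must exceed L at both Week 12 and Week 24.
- Helped eyes shift by +δ and harmed eyes by −δ, with δ = 4s or 6s.
- Baseline is the mean of three measurements. SAP 3.2 sets a mean; Table 2 schedules three baseline visits for most visual function tests.

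Each change then has variance s²(1 + 1/3) = 1.333s². The Week 12 and Week 24 changes have covariance s²/3, so their correlation is 0.25. The chance q that a helped eye exceeds L at both visits is 0.748 for δ = 4s and 0.995 for δ = 6s.

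- Expected gains = 36 × (fraction helped) × q
- Expected losses = 36 × (fraction harmed) × q
- Mean change = (helped − harmed) × δ
- SD of change = √[1.333s² + (helped + harmed)δ² − mean²]

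For 30% helped: 36 × 0.30 × 0.748 = 8.1 and 36 × 0.30 × 0.995 = 10.7.

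| Helped / harmed | Gains of 36 | Losses of 36 | Mean change | SD of change |
|---|---|---|---|---|
| 30% / 0% | 8.1 to 10.7 | 0 | 1.2s to 1.8s | 2.2s to 3.0s |
| 30% / 30% | 8.1 to 10.7 | 8.1 to 10.7 | 0 | 3.3s to 4.8s |
| 30% / 50% | 8.1 to 10.7 | 13.5 to 17.9 | −0.8s to −1.2s | 3.7s to 5.4s |

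The protocol's proportion does not move across the rows. The SAP's mean and SD do.

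**Step 3. Could chance alone fill the tails?** With no true change, the probability of crossing L upward at both visits is 0.46% with a single baseline and 0.03% with a mean of three. For ERG, with one screening value and one Week 24 value, it is 2.5% in each direction. Chance crossings are therefore not the main issue for visual function.

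**Step 4. Have both tails been seen?** Protocol 4.1.3 says that in the first trial "6 of the 12 participants benefitted with improved visual function". Protocol 4.1.5.5 reports "deterioration in acuity in 2 of the 12 participants in our previous clinical trial", apparently the same trial. 2/12 = 16.7%, exact 95% CI 2.1% to 48.4%.

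**The case against.** The case on the other side is substantial, and much of it stands.

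- **No decision rule.** A reader might infer that a vector harming some eyes would be declared effective. The documents do not support this. Protocol 5.10.3.1 makes the analysis descriptive, SAP 1.2 says there was no formal hypothesis testing, and Protocol 5.10.3.3 sets no threshold and reports measures individually as well as in aggregate.
- **The SAP no longer computes the rule.** Its minima, maxima and individual plots show both directions, and with at most 36 participants a losing eye can be seen. But nothing requires such eyes to be counted, and the protocol criterion still stands in v7.0, on which the SAP is based.
- **Losses are not ignored.** Protocol 5.11.3.5 requires clinically significant test abnormalities to be recorded as adverse events until the end of the trial, and 5.11.3.1 includes worsening of baseline disease. SAP 5.2 tabulates adverse events by severity and by relationship to product and to surgery. That captures late, non-acuity and surgical losses, but for test results no numerical limit says when a loss qualifies.
- **The earlier trial does not transfer.** A reader might carry 2/12 forward and expect 36 × 2/12 = 6 losses here. That trial concerned another gene (RPE65) and another vector (AAV2/2), and the size, timing and persistence of the losses are not given. Nor is it stated that the 6 gains met the present rule. The figures show only that both tails can occur.

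**Conclusion.** The concern holds in limited form. The protocol's aggregate efficacy measure counts one direction, and no document defines a matching count of losses. Losses under 15 letters, after Week 6, due to surgery alone, or on tests other than acuity have no defined threshold. The SAP's summaries and plots can reveal them but do not count them, and the signed change from baseline is conditional.

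The size cannot be fixed from the documents. Under the assumptions in the working, about 8 to 11 gains in 36 would be reported whether the uncounted losses were none or as many as 13 to 18. The qualitative result, that the gain proportion cannot register harm in other eyes, needs none of those assumptions. The consequence is an incomplete descriptive report, not an invalid test or a false declaration of efficacy.

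**What to change.** 1. In Protocol 5.5.2 and 5.10.3.3 and SAP 6.2, classify each eye on each test as improved, unchanged or worsened, with the same limit in both directions. Report the proportions side by side for treated and fellow eyes, by dose level and age group.
2. For visual function tests, keep the requirement of two consecutive assessments, using Weeks 12 and 24. For ERG use Week 24 only, because Table 2 schedules no other post-treatment ERG.
3. Make the signed change-from-baseline summary in SAP 6.2 mandatory.
4. Reconcile Protocol 5.5.2 and 5.10.3.3 with SAP 6.1. If test-retest limits stay dropped, tabulate acuity gains and losses symmetrically, at least 5, 10 and 15 letters each way. A table for both eyes also suits the treated-against-untreated comparison that SAP 6.1 gives as its reason for the change.

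The cost is protocol and SAP wording and one more column per table, from assessments already scheduled. The efficacy summary may look less favourable.

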1.4 Roles and responsibilities

Agreements that include detailed roles and responsibilities will be in place between participating sites and MeiraGTx UK II Ltd.

These membership lists are correct at the time of writing; please see terms of reference documentation in the TMF for current lists.

[figure not shown]

OCT	Optical Coherence Tomography
PCR	Polymerase Chain Reaction
PERG	Pattern Electroretinogram
PHI	Protected Health Information
PI	Principal Investigator
PIS	Participant Information Sheet
QA	Quality Assurance
QALY	Quality Adjusted Life Year
QC	Quality Control
qds	quarter die sumendus (four times daily)
QOL	Quality of Life
QP	Qualified Person for release of ATIMP
rAAV	Recombinant adeno associated virus

REC	Research Ethics Committee
RG	Research grade
RGF	Research Governance Framework
RNA	Ribonucleic acid
RPE	Retinal Pigment Epithelium
SAE	Serious Adverse Event
SAP	Statistical Analysis Plan
SAR	Serious Adverse Reaction
SD-OCT	Spectral Domain Optical Coherence Tomography
SOP	Standard Operating Procedure
SSA	Site Specific Approval
SSAR	Suspected Serious Adverse Reaction
SUSAR	Suspected Unexpected Serious Adverse Reaction
SV40	Simian virus 40
TMF	Trial Master File
tRNA	Transfer ribonucleic acid
UAR	Unexpected Adverse Reaction
█	█
UK	United Kingdom of Great Britain & Northern Ireland
USA	United States of America
vg	Viral Genomes
█	█
WT	Wild type

4 Introduction

